3.3 Planned Sensitivity Analyses

[figure not shown]
In addition to the primary as-assigned analysis of the endpoint, a per-protocol analysis of the primary endpoint will be performed in which patients that failed to start their assigned study transfusion in compliance with the protocol will be excluded. An as-exposed analysis will not be performed.

4. Type I error rate and power

The long-run operating characteristics were estimated by generating study data to reflect different treatment effect sizes. The simulated study dataset was evaluated according to the stopping rule and analysis plan described above. For each effect size, 1000 simulated datasets were analyzed. A Type I error occurred if the study asserted efficacy when in fact there was no treatment effect. For each treatment effect, the Type I error rate was calculated as the proportion of null-effect studies in which the error occurred. A Type II error occurred if the study failed to assert efficacy when there was a beneficial treatment effect. For each treatment effect, power was calculated as the proportion of studies that did not result in a Type II error.

The study endpoint for control subjects was simulated to match the outcomes in the control arm of a recent clinical trial.⁶ In each simulation setting, the distribution for the treatment arm was calculated by adjusting the control arm outcome distribution according to the setting-specific treatment effect size and data generation model.

These simulations demonstrated that enrollment of 1000 patients (500 patients in the intervention group and 500 patients in the control group) would provide 80% power to detect an adjusted odds ratio of ≤ 0.73 . Some trials orient the ordinal outcomes scale in the reverse direction, with an odds ratio greater than 1.0 indicating benefit from the intervention. With reversal of the ordinal outcomes scale, enrollment of 1000 patients would provide 80% power to detect an adjusted odds ratio ≥ 1.37 . The simulations also demonstrated that the type I error rate was bounded below 0.05. The figure below is the estimated power curve for the trial design.

5 Analysis plan for additional analyses of the primary endpoint

5.1 Quantification of donor plasma efficacy

Quantification of donor plasma efficacy. The impact of the binding and neutralization levels of the donor plasma on the primary endpoint will be estimated with two ordinal regression models. In the first, the model will include the same covariates listed for the primary endpoint analysis with the addition of a measure of donor plasma binding level. Similarly, in the second model, a measure of donor plasma

neutralization levels will be added to the models. The variables will be included into the models as a restricted cubic spline with three knots in order to capture potential non-linear associations with the outcome. For observations in the control arm, binding and neutralization values will be set to zero.

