5. STUDY INTERVENTIONS

5.1 Treatment of Study Participants

A summary of the trial's schedule of events is included in Appendix A.

Timing of study procedures is based on the time of initiation of the study product infusion, which is defined as "Time 0". Study Day 1 is defined as the calendar day of study product infusion. For patients who are randomized but do not receive study product, time of randomization will be considered "Time 0" and Study 1 will be the calendar day of randomization. For most patients, randomization and study product infusion will occur on the same day; in the event the study product is infused on a different calendar day than randomization, Study Day 1 is defined as the day on which study product is infused. "Baseline status" represents the patient's status immediately prior to study infusion, and baseline variables should represent information available before and as close as possible to initiation of the study infusion. The primary outcome will be assessed on Study Day 15 which corresponds to 2 weeks (14 days) after the receipt of the study infusion.

Transfusion of convalescent plasma or placebo will be administered as a single dose by clinical or research personnel while the patient is hospitalized and within 24 hours of randomization. Participants randomized to active treatment will receive 1 unit of convalescent plasma, which has a volume of 200-399 ml infused intravenously. Patients randomized to placebo will receive 250 ml of lactated Ringer's with multivitamin additives infused intravenously. The duration of infusion is recommended to be between approximately 1 hour and 3 hours (at the discretion of the provider), with the specific rate of infusion determined by the site investigator based on an assessment of how quickly the participant can safely receive the intravascular volume load.

Study personnel will monitor patients for adverse reactions to the transfusion while the patient is in the hospital for 72 hours following the infusion; that is transfusion adverse reaction monitoring will be continued until Study

Day 4. For patients who are discharged prior to Day 4, study personnel will obtain safety outcomes from the patient or surrogate via telephone follow-up scheduled at Day 8. Research personnel will also assess patients at Day 15 and Day 29; these assessments will be completed by phone if the patient has been discharged from the hospital.

Screening, consent, and baseline

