5.2 Convalescent Plasma Group

Patients randomized to the active treatment arm will receive a single dose of 1 unit (200-399 ml) of convalescent plasma infused intravenously per site institutional policy governing blood product transfusions. Convalescent plasma used in this trial will be ABO compatible with the participant's blood type. The convalescent plasma will be supplied to enrolling sites for the trial. Quantitative SARS-CoV-2 antibody testing will be completed at Vanderbilt University Medical Center on convalescent plasma used in the trial. Plasma that is believed to be neutralizing will be used in this trial and will be prioritized based on neutralizing capabilities. Only plasma that contains anti-SARS-CoV-2 antibodies at a level above the threshold for neutralization will be used in the trial.

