8.5 Analysis plan for additional analyses of the primary endpoint

8.5.1 Quantification of effect of donor plasma characteristics on treatment efficacy

The impact of the antibody levels and neutralization activity of the donor plasma on the primary endpoint will be estimated with ordinal regression models. The models will include the same covariates listed for the primary endpoint analysis, except the treatment assignment variable will be replaced with either (a) a measure of donor plasma antibody level or (b) a measure of donor plasma neutralization. Both variables will be included in models as a restricted cubic spline in order to capture potential non-linear associations with the outcome.

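### The donor-plasma titre models have no calendar-time term, so a titre effect that was never randomized may be confounded by time, in either direction

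*SAP*

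**What the plan says.** **The models.** SAP 5.1 specifies two ordinal regressions for the primary endpoint. The first takes the primary covariate list "with the addition of a measure of donor plasma binding level"; the second does the same with a neutralization level. Each measure (called titre below) enters as a "restricted cubic spline with three knots in order to capture potential non-linear associations with the outcome". For placebo patients, "For observations in the control arm, binding and neutralization values will be set to zero".

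**The covariates.** The list in SAP 3 is treatment, age, sex, baseline SOFA, baseline ordinal score, time from symptom onset, and site. It contains no date.

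**The protocol version.** Protocol 8.5.1 keeps the same covariates, "except the treatment assignment variable will be replaced with either (a) a measure of donor plasma antibody level" or a neutralization measure. The SAP adds titre to a list that includes treatment, whereas the protocol substitutes titre for treatment. That conflict is a separate point and must be reconciled, but neither version has a calendar term.

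**Supply.** Protocol 5.2 says: "Plasma that is believed to be neutralizing will be used in this trial and will be prioritized based on neutralizing capabilities". It also restricts use to units above a neutralization threshold. Protocol 3.3 has plasma coming through blood donation groups, in the plural. The summary of changes for version 6.0 lists the prioritization sentence as new and gives multiple donation centers as the reason for the supply change.

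**Possible drift in outcomes.** Protocol 5.4 leaves antivirals and immunomodulators, including corticosteroids, to treating clinicians. The same summary of changes adds exclusions for previous infection and vaccination, and widens the passive-immunity exclusion to name monoclonal antibodies.

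**Data available.** Protocol 7.1 lists the date and time of randomization. A unit is "1 unit of convalescent plasma, which has a volume of 200-399 ml infused intravenously" (Protocol 5.1); Protocol 7.2 lists the date and time of the infusion but no volume.

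**The concern.** Randomization protects the comparison of plasma with placebo. It does not protect the comparison of plasma patients who received strong units with those who received weaker ones. Which unit a patient gets depends on what is in stock and how it is prioritized when the patient enrols, and both can change over the trial. Background treatment and the eligible population can change over the same period. If both move, titre partly stands in for calendar time. Keeping the treatment indicator does not remove this, because that indicator carries no information on time within the plasma arm.

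This is the only specified outcome analysis of whether more donor antibody works better, which is the natural question after a null overall result. Confounding by time could hide a real gradient or produce a false one. Neither document says that the gradient is non-randomized.

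**Working it through.** The documents state no power or precision for this analysis, so there is no figure of theirs to reproduce. What follows shows how large the bias could be under stated assumptions. It uses the SAP version of the model (treatment kept) with titre linear on the log scale.

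**Inputs from the documents.** 500 plasma patients (SAP 4). Likelihood-ratio threshold 7 (SAP 3), equivalent to |z| = sqrt(2 ln 7) = 1.973. SAP 5.1 sets no threshold of its own, so 7 is borrowed.

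**Assumptions.** Uniform accrual, so calendar time scaled 0 to 1 has SD 1/sqrt(12) = 0.2887. Log-linear outcome trend. Normal log titre, so the 10th-90th percentile distance is 2.563 SD. Outcome spread 1 - sum(p^3) = 0.93; the control distribution is not in the documents.

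**Step 1: standard error.** Per SD of titre: sqrt(3/(500 x 0.93)) = 0.0803. For the 10th-90th percentile contrast: 0.0803 x 2.563 = 0.206.

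**Step 2: bias when titre has no effect.** Spurious log OR per SD = r x 0.2887 x ln(T), where r is the titre-time correlation and T is the last-to-first odds ratio for a worse outcome.

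| T | r | log OR per SD | OR per SD | OR, 10th-90th | Bias / SE |
|---|---|---|---|---|---|
| 0.8 | -0.3 | 0.019 | 1.02 | 1.05 | 0.2 |
| 0.7 | -0.6 | 0.062 | 1.064 | 1.17 | 0.8 |
| 0.5 | -0.8 | 0.160 | 1.174 | 1.51 | 2.0 |
| any | 0 | 0 | 1.00 | 1.00 | 0 |
| 1.0 | any | 0 | 1.00 | 1.00 | 0 |

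If r is positive the ORs invert: 1/1.05 = 0.95 to 1/1.51 = 0.66, a false benefit of higher titre.

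**Step 3: simulation check.** 1000 patients, treatment kept, control titre 0, SD of log titre 0.5, r = -0.5, T = 0.6, an assumed seven-category distribution, 60 datasets per setting.

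- *No true titre effect.* Without time the mean coefficient was +0.169 per log unit. The formula gives 0.5 x 0.2887 x 0.511 / 0.5 = 0.147, and the Monte Carlo error is about 0.148/sqrt(60) = 0.019. |z| exceeded 1.973 in 15% of datasets. With time added the coefficient was +0.017 and the rate 2%.
- *True slope -0.30, with 3% partial infusions.* The estimate was -0.136 without time and -0.281 with it.

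With 60 datasets the percentages are rough; the direction is clear.

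**Step 4: unit volume.** The permitted range is 399/200 = 2.0-fold. If volume is uniform over it and independent of titre (assumptions), SD of log volume is 0.197. Titre alone then keeps s^2/(s^2 + 0.197^2) of the variance of log antibody amount: 80%, 93% and 96% for a log-titre SD s of 0.4, 0.7 and 1.0. The corresponding SE inflation is about 12%, 4% and 2%. At s = 0.2 it keeps 51%.

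**The case against.** **The strongest units go out first.** A reader might infer this from Protocol 5.2. The text does not say it. Prioritizing by neutralizing capability could equally mean choosing which units enter the trial. No dispensing order, fixed stock or decline in titre is stated, and resupply from several groups could break any trend. This objection stands, so the direction of any bias is unknown and the titre effect can only be said to be possibly confounded. The need for a date term does not depend on the direction.

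**Both conditions must hold.** The outcome trend has to remain after adjustment for age, SOFA, baseline score, symptom duration and site. That also stands. The upper end of the range needs the odds to halve and a correlation of -0.8.

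**Comparison with the design effect.** A reader might set the spurious odds ratio beside the detectable 0.73 (1.37 reversed). That figure is for the randomized contrast in 1000 patients. The proper yardstick is the titre contrast's own standard error, for which 80% power at a likelihood ratio of 7 needs an OR of about exp((1.973 + 0.842) x 0.206) = 1.8.

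**Delivered dose.** A reader might conclude that ignoring volume and incomplete infusions invalidates the titre slope. Volume independent of titre costs precision, usually little, and essentially does not bias a linear slope. Making infused volume the main exposure could do harm. Under Protocol 5.6 infusions stop for reactions and deterioration, so delivered amount is a post-randomization quantity and could create a false dose-benefit gradient. SAP 3.3 also rules out an as-exposed analysis. Per-kilogram exposure and adjustment for ABO group have no supporting figure in the documents.

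**Secondary importance.** The analysis is additional and does not touch the primary result, its error rate or the mortality stopping rule. True, but the remedy uses data already collected.

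**Conclusion.** The point holds as a risk of confounding, not as demonstrated bias. The titre gradient is not randomized, neither model adjusts for calendar time, and the documents describe ways in which both titre mix and outcomes could move during accrual. Under the assumed values a null titre would show an odds ratio of 1.05 to 1.51 across its 10th-90th percentiles (0.2 to 2 SE), or the inverse if the correlation is positive. There is no bias if either the correlation or the trend is zero. Those two quantities, the titre spread and the outcome distribution are assumptions, because the documents give none of them. The documents do not support saying that the titre effect is confounded, or that volume makes it seriously imprecise; only a narrow titre spread would do the latter, and the spread is not given. The change is worth making before unblinding because it is cheap and this is the only planned outcome analysis of donor antibody level.

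**What to change.** In SAP 5.1 and Protocol 8.5.1, add randomization date as a restricted cubic spline to both donor-plasma models, and state that the titre result is non-randomized and exploratory. No new data are needed.

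**Cost.** About two extra parameters with a three-knot spline, and a wider interval if titre and date are correlated. With the treatment term kept and a trend shared by both arms, the concurrent controls help to estimate the trend, and the SE grows by about 1/sqrt(1 - r^2/2): 2% at r = -0.3, 10% at -0.6 and 21% at -0.8. The simulation agrees at r = -0.5 (0.160 to 0.171, or 7%).

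**Optional.** Keep titre as the main exposure. Where unit volume is available, show titre times the volume of the unit issued, which is fixed before infusion, as a sensitivity analysis. Do not use the volume actually infused as the main exposure.

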5.2 Effect modification analyses of the primary outcome

The degree to which pre-specified baseline variables modify the treatment effect will be examined with tests of statistical interaction in a proportional odds regression model. Independent variables will include study group assignment, the potential effect modifier of interest, the interaction between the two, and the same pre-specified covariates used in the primary model. Presence of effect modification will be assessed by reference to the LR for the interaction term, with values greater than 6 considered to suggest a potential interaction and values greater than 7 considered to confirm an interaction.

We will examine whether the following pre-specified baseline variables modify the effect of study group on the primary outcome:

- Baseline recipient (trial participant) antibody quantification
- Baseline COVID scale
- Baseline SOFA
- ICU/ward enrollment location
- Age
- Race/ethnicity
- Duration of symptoms prior to randomization
- Mechanical ventilation status at baseline

6 Analysis plan for secondary endpoints

The analyses for secondary endpoints will be intent-to-treat. The following is a table of secondary endpoints and a column indicating the planned analysis.

Outcome	Type	Analysis
All-location, all-cause 14-day mortality (assessed on Study Day 15)	Binary	Logistic regression
All-location, all-cause 28-day mortality (assessed on Study Day 29)	Binary	Logistic regression
Survival through 28 days	Time-to-event	Proportional hazards regression
Time to hospital discharge through 28 days	Time-to-event	Multistate model with death as a competing risk

Time to recovery (defined as time from randomization to the earlier of final oxygen receipt in the hospital or hospital discharge)	Time-to-event	CPM with logit link
COVID-19 7-point Ordinal Clinical Progression Outcomes Scale on Study Day 3, 8 and 29	Ordinal	CPM with logit link
Oxygen-free days through Day 28	Ordinal	CPM with logit link
Ventilator-free days through Day 28	Ordinal	CPM with logit link
Vasopressor-free days through Day 28	Ordinal	CPM with logit link
ICU-free days through Day 28	Ordinal	CPM with logit link
Hospital-free days through Day 28	Ordinal	CPM with logit link

6.1 Ordinal outcomes

Ordinal secondary outcomes will be analyzed using the same model described for the primary endpoint. Similar steps to evaluate model fit and overly influential observations will be performed.

6.2 Binary outcomes

Binary secondary outcomes will be analyzed using multivariable logistic regression models with the same pre-specified covariates as the primary endpoint. To assess model calibration and overly influential observations, graphical displays of calibration and DFBETAS will be created.

6.3 Time to event outcomes

Time to event outcomes will be analyzed with a proportional hazards regression model. The key result of the analysis is an estimate of the treatment effect hazards ratio. The same set of covariates used for the adjusted analysis of the primary endpoint will also be included in the analysis of secondary time-to-event endpoints. Model fit will be assessed with Schoenfeld residuals and with leave-one-out diagnostics like DFBETAS. The proportional odds assumption will be evaluated with graphical displays. Deviations from proportionality will trigger sensitivity analyses.

6.4 Outcomes with a competing risk of death

Some secondary outcomes, like the primary outcome, incorporate death as part of the scale. Others, such as length of hospital stay, do not. Because death censors length of stay, it is a competing outcome. Outcomes with a competing risk of death will be analyzed with a multi-state model. Both the instantaneous risk and cumulative risk of the outcome will be reported.

7 Safety Outcomes and Adverse Events

The frequency and description of safety outcomes and adverse events will be reported for all enrolled patients grouped by treatment assignment. The association between treatment received and safety

outcomes between groups will be estimated without covariate adjustment. The following table lists the safety outcomes and the planned analyses.

Outcome	Type	Analysis
Receipt of renal replacement therapy	Binary	Risk difference
Documented venous thromboembolic disease (DVT or PE)	Binary	Risk difference
Documented cardiovascular event (myocardial infarction or ischemic stroke)	Binary	Risk difference
Transfusion reaction	Binary	Risk difference
Transfusion related acute lung injury (TRALI)	Binary	Risk difference
Transfusion associated circulatory overload (TACO)	Binary	Risk difference
Transfusion related infection	Binary	Risk difference

8 Definition of the Primary Outcome

The primary outcome is patients' clinical status 14 days after randomization (measured on Study Day 15) as assessed with the seven-category COVID Ordinal Outcome Scale:

- Not hospitalized without limitation in activity
- Not hospitalized with limitation in activity
- Hospitalized not on supplemental oxygen
- Hospitalized on supplemental oxygen
- Hospitalized on non-invasive ventilation or high-flow nasal cannula
- Hospitalized on invasive mechanical ventilation or extracorporeal membrane oxygenation
- Death

While patients are in the hospital, primary outcome assessment will be performed by review of the electronic health records. For patients discharged prior to 14 days after randomization, study staff will call patients or their surrogates to obtain the patients' clinical status for primary outcome assignment.

9 Definition of SOFA Score

The SOFA score at baseline (pre-randomization) will be used as a co-variable in the regression models for the primary and secondary outcomes. The SOFA score will be calculated using the definitions based on the Third International Consensus Definitions for Sepsis and Septic Shock (Sepsis-3). The SOFA score will be calculated using data available in the 24 hours prior to randomization. We record the following data for SOFA score calculation: lowest SpO₂ and FIO₂ at the time of the lowest SpO₂ measurement; lowest platelet count; highest total bilirubin concentration; lowest Glasgow Coma Score; lowest mean arterial pressure; receipt and dose of inotropes/vasopressors, including dobutamine, dopamine, epinephrine, norepinephrine, phenylephrine, and vasopressin; highest creatinine; highest INR.

For calculation of the respiratory component of the SOFA score, if recorded, FiO₂ will be used in the calculation of the S:F ratio. If no FIO₂ is recorded, FiO₂ will be estimated with the following equation: 0.21 + (supplemental oxygen flow rate in liters/minute) * 0.03. Respiratory SOFA score will be classified by SpO₂ and SpO₂:FiO₂ ratio according to the table below based on the validated technique described by Pandharipande:

Respiratory SOFA Score assignment based on SpO₂ and FIO₂ values when no PaO₂ is recorded	
Values	Respiratory SOFA Score Assignment
SpO ₂ ≥95% and FiO ₂ =0.21 (room air)	0
If SpO ₂ <95% or FiO ₂ >0.21, calculate the SpO ₂ :FiO ₂ ratio and assign respiratory SOFA score based on the thresholds below:	
SpO ₂ : FiO ₂ ≥357	1
SpO ₂ : FiO ₂ ≥214 and <357	2
SpO ₂ : FiO ₂ ≥89 and <214	3
SpO ₂ : FiO ₂ <89	4

When no S:F ratio is available, the respiratory SOFA score will be imputed as the median observed value in the patients in the trial with non-missing values.

10 Definition of Secondary Outcomes

10.1 All-location, all-cause 14-day mortality

All location, all cause 14-day mortality is defined as death between randomization and 14 days after randomization from any cause and in any location, including after discharge from the index hospitalization. Data on death will be collected from the electronic health record during the hospitalization and then from telephone calls to the patient or surrogate after discharge on Study Day 8, 15 and 29.

